4.2.5. Multiple Comparisons/Multiplicity

All statistical hypothesis tests and confidence intervals will be two-sided. To maintain an overall type I error rate of 0.05, as there are two linzagolix versus placebo comparisons, Bonferroni corrected p-values will be produced (raw p-values will be multiplied by two prior to comparing to 0.05), along with corresponding 97.5% confidence intervals.

The two co-primary efficacy endpoints will be clinically meaningful reduction from baseline over the last 28 days of randomized treatment up to the Month 3 visit (i.e., the 4-week period preceding the Month 3 visit) in the mean daily assessment of DYS and of NMPP measured on a VRS, along with a stable or decreased use of analgesics for EAP.

The primary objective will be assessed by testing the following two-sided hypotheses for each co-primary endpoint, for each linzagolix group versus placebo separately:

Null hypothesis (H0): There is no difference in the odds of subjects meeting the primary endpoint for the active treatment group compared to placebo, that is, the odds ratio (OR) equals 1.

Sponsor:	ObsEva		
Protocol:	18-OBE2109-003		
Document Version No.:	V5.0		

H0: OR =1

Alternative hypothesis (H1): There is a difference in the odds of subjects meeting the primary endpoint for the active treatment group compared to placebo, that is, the OR is not equal to 1.

H1: OR ≠ 1

Where odds are equal to the proportion of subjects meeting the endpoint divided by proportion of subjects not meeting the endpoint.

Each linzagolix group will need to demonstrate a statistically significant difference for both co-primary endpoints for the group to be considered more efficacious than placebo, thus maintaining an overall type I error rate of 0.05.

For each linzagolix group that is statistically significantly more efficacious than placebo for the co-primary endpoints, a fixed-sequence testing strategy shall be used within the group to test the ranked secondary endpoints as ordered in Section 2.5.1.2, to maintain the family-wise type I error rate. That is, the comparison for each linzagolix group versus placebo for each ranked endpoint will only be declared statistically significant different if the raw p-value multiplied by two is less than or equal to 0.05 for that endpoint and for all preceding endpoints for that dose versus placebo.

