4.2.8. Missing, Unused, and Spurious Data

4.2.8.1. Efficacy Endpoints Missing Data

Summary statistics will be based primarily on non-missing values. The planned statistical analyses aim to estimate the efficacy of linzagolix versus placebo while under randomized treatment and therefore lack of data after treatment discontinuation will not be considered as missing for these analyses.

Subjects who cannot be assessed as responders for the co-primary efficacy endpoints, e.g. due to lack of on treatment pain data (i.e. subjects who received less than 28 days of treatment), will be considered as non-responders. In addition, for endpoints assessing the numeric change from baseline, such subjects will be assigned a change from baseline of zero. It is expected that very few subjects will be affected by these rules.

There may be missing data during the screening period and whilst under treatment, for example, missed days of completing the eDiary. The primary analyses will use observed data only in such cases provided that a minimum number of completed daily eDiary entries are available. This effectively assumes that the individual values such as daily eDiary assessments (observed or not) are independent of being missing.

Further details on the handling of missing values and the methods and planned sensitivity analyses to check the robustness of the analysis results under alternative assumptions with regards to missing data are provided in the analyses sections. As additional analyses, in order to estimate the effect of treatment policy, a reference based multiple imputation approach will be used for the co-primary endpoints for subjects who discontinue the study early under the assumption that the efficacy of the linzagolix treated subjects gradually transitions to that observed in the placebo subjects.

Missingness Assumptions:

Missing At Random (MAR): Missingness is independent of unobserved outcomes given observed data. Subjects with missing data can be modeled based on similar subjects with available data if we account in the model for relevant observed factors.

Missing Not At Random (MNAR): The probability of missingness depends on the unobserved outcome and cannot be predicted only based on observed data.

Multiple Imputation Methodology:

Multiple imputation inference involves three distinct steps:

Sponsor:	ObsEva		
Protocol:	18-OBE2109-00	18-OBE2109-003	
Document Version No.:	V5.0		

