Intercurrent events: Increased use of EAP analgesia is a non-response in the endpoint definition. Treatment discontinuations are assessed up to the time of discontinuation. Randomized treatment will be considered, regardless of lack of compliance to treatment or treatment assignment errors. The clinical question of interest is based on a while-on-treatment strategy for discontinuation and composite strategy for analgesic use. Lack of compliance to treatment and treatment assignment errors are handled using a treatment policy strategy.

The "while-on-treatment strategy" was chosen for the intercurrent event of discontinuation of treatment for the co-primary endpoints based on the recommended strategies for addressing intercurrent events in the (then draft) ICH E9 (R1) guideline.

Sponsor:	ObsEva	ObsEva		
Protocol:	18-OBE2109-00	18-OBE2109-003		
Document Version No.:	V5.0 Document Date: 13-JUN-2022			

The response to treatment prior to the occurrence of the patient discontinuing treatment is of clinical interest for a symptomatic treatment of endometriosis-associated pain. Patients and prescribers are generally interested in what happens when a patient actually takes (and can take) the treatment. This corresponds most directly to the "while on treatment" strategy for treatment discontinuation. Of note, a comparison of patient disposition and discontinuation rates will also constitute an important aspect when interpreting the study results. In addition, a "while-on-treatment" strategy for efficacy aligns with the analysis of adverse events, which are also considered while on treatment. Moreover, as endometriosis-related pelvic pain is measured repeatedly each day, the variable can be readily calculated for the 28-day period up to the point of discontinuation and the value up to the time of discontinuation can be considered to account for the intercurrent event.

For each of the co-primary endpoints, the criterion for defining a subject as a responder over the last 28 days of randomized treatment up to the Month 3 visit will include a reduction of X or greater from baseline in pain, where X was determined by a meaningful change threshold estimation using appropriate anchors as described in Section 4.6.1, as well as stable or decreased use of analgesics for EAP. Results of the meaningful change threshold estimation 4.6.1.3.

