Mean pelvic pain scores for DYS and for NMPP will be calculated by averaging over the corresponding 28 calendar days immediately prior to and including the day of the Month 3 visit. DYS will use days with uterine bleeding, defined as those days on which the subject records any uterine bleeding or spotting in the subject eDiary; NMPP will use days with no uterine bleeding. If a subject's mean score for DYS is undefined numerically because her daily eDiary reports indicate that she did not experience uterine bleeding on any days during the 28 calendar day period, then the mean score for DYS will be set equal to zero (which reflects the absence of any DYS during that reporting time period). Similarly, if a subject's diary reports indicate that she only experienced days with uterine bleeding during the period, then the mean score for NMPP will be set equal to zero. For subjects who discontinue treatment prior to Month 3, the last available observations prior to discontinuation will be used, in order to estimate the treatment effect while under treatment, that is the 28 calendar days immediately prior to and including the last dose date. The baseline mean overall pelvic pain scores for DYS and NMPP will be calculated by averaging over the two baseline menstrual cycles (as defined in section 4.2.10), which may not be exactly 28 days each. For both DYS and NMPP, responses of "None," "Mild," "Moderate," and "Severe" will be assigned a score of 0, 1, 2, and 3, respectively.

For the assessment of stable or decreased use of analgesics for EAP (assessed separately for DYS and NMPP), the analgesic use for any defined period will be based on the mean of the total pill count for each class of rescue analgesics (endometriosis-associated). The total pill count for each class of rescue analgesic is the sum of the pill count of the corresponding class of rescue analgesic, as reported in the eDiary during the time period of interest. Baseline analgesic use will be calculated as the mean of the daily pill count of analgesics over the two baseline menstrual cycles (as defined in section 4.5.2). For the purposes of determining a stable or decreased use of analgesics, the averaging will be done over the same calendar days as used for the pelvic pain scores (i.e. for DYS days with uterine bleeding, defined as

Sponsor:	ObsEva		
Protocol:	18-OBE2109-003		
Document Version No.:	V5.0	Document Date:	13-JUN-2022

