Subjects whose response cannot be assessed for the co-primary efficacy endpoints, e.g. due to lack of on treatment pain data (i.e. subjects who received less than 28 days of treatment), will be considered as non-responders. In addition, for outputs presenting the numeric change from baseline, such subject will be assigned a change from baseline of zero. It is expected that very few subjects will be affected by these rules.

There may be missing data during the screening period and whilst under treatment, for example, missed days of completing the eDiary. The primary analyses will use observed data only in such cases, provided that a minimum number of completed daily eDiary entries are available. This effectively assumes that the individual values such as daily eDiary assessments (observed or not) are independent of being missing. Subjects who have less than the minimum number of days available will be excluded from the analysis. This is valid under the assumption that such data is MAR, conditional on the baseline value.

The required minimum number of completed daily eDiary entries will be set to 12 days of each 28-day period (two Baseline menstrual cycles and the 28-day period prior to Month 3), i.e., 43% of non-missing assessments for the primary analysis, consistent with the use of 3 days per week as the minimum number of completed diary entries as suggested in recent research ((Griffiths & al, 2018), (Cappelleri & Bushmakin, Biopharmaceutical Report, 2020), (Cappelleri & Bushmakin, Biopharmaceutical Report, 2020), (Cappelleri & Bushmakin, Biopharmaceutical Report, 2020), Cappelleri & Bushmakin, Biopharmaceutical Report, 2020), (Cappelleri & Bushmakin, Biopharmaceutical Report, 2020), completed daily eDiaries for DYS, NMPP and analgesic use.

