7. APPENDICES

7.1. Appendix A: Analgesic change during treatment period

Use of No Analgesics at Baseline					
Analgesic used during Screening	Analgesic dose status at end of study	Assessment of Change			
	None**	Stable/Decrease			
None	Narcotic analgesic and/or ibuprofen is started	Increase			
Use of Only Ibuprofen at Basel	ine				
Analgesic uses at Baseline	Analgesic dose status at end of study	Assessment of Change			
	Dose stopped, decreases, or is stable**	Stable/Decrease			
ibuprofen	Dose increases by 15% or more	Increase			
	Narcotic analgesic is substituted or added	Increase			
Use of Only Narcotic Analgesic	at Baseline				
Analgesic uses at Baseline	Analgesic dose status at end of study	Assessment of Change			
	Dose stopped, decreases, or is stable**	Stable/Decrease			
Narcotic analgesic	Dose stopped and ibuprofen substituted (any dose)	Stable/Decrease			

Sponsor:	ObsEva		
Protocol:	18-OBE2109-00	3	
Document Version No.:	V5.0	Document Date:	13-JUN-2022

	Dose decreases and ibuprofen added (any dose)	Stable/Decrease
	Dose stable and ibuprofen added (any dose)**	Increase
	Dose increases by 15% or more	Increase
Use of Ibuprofen and Narcotic	Analgesic at Baseline	
Analgesic uses at Baseline	Analgesic dose status at end of study	Assessment of Change
	Ibuprofen dose stops + narcotic analgesic use stops, decreases, or is stable**	Stable/Decrease
	Ibuprofen use stops + narcotic analgesic dose increases by more than 15%	Increase
	Ibuprofen dose decreases + narcotic analgesic use stops, decreases, or is stable**	Stable/Decrease
ibuprofen + narcotic analgesic	Ibuprofen dose decreases + narcotic analgesic dose increases by more than 15%	Increase
	Ibuprofen dose stable + narcotic analgesic use	Stable/Decrease
	stops, decreases, or is stable**	
	Ibuprofen dose stable + narcotic analgesic dose	Increase
	increases by more than 15%	

Sponsor:	ObsEva		
Protocol:	18-OBE2109-003		
Document Version No.:	V5.0	Document Date:	13-JUN-2022

Ibuprofen dose increases by more than 15% + narcotic analgesic use stops	Stable/Decrease
Ibuprofen dose increases by more than 15% + narcotic analgesic dose decreases	Stable/Decrease
Ibuprofen dose increases by more than 15% + narcotic analgesic dose is stable**	Increase
Ibuprofen dose increases by more than 15% + narcotic analgesic dose increases by 15% or more	Increase

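### Does the DYS analgesic test break down for a woman with no bleeding day in the 28-day window?

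*SAP*

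**What the plan says.** A DYS responder at Month 3 needs a fall of at least 1.10 points in mean pain on bleeding days (SAP 4.6.1.3) and an analgesic status other than increase (SAP 4.6.2.1.1).

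- **Pain.** If the diary shows no bleeding "on any days during the 28 calendar day period, then the mean score for DYS will be set equal to zero". The mirror rule for non-menstrual pelvic pain (NMPP) applies when the diary shows that "she only experienced days with uterine bleeding during the period, then the mean score for NMPP will be set equal to zero".
- **Analgesics.** Use is the mean of a total pill count per drug class, and the total is defined as a sum over the period. The days are restricted: "the averaging will be done over the same calendar days as used for the pelvic pain scores (i.e. for DYS days with uterine bleeding", and non-bleeding days for NMPP. The tabulations in SAP 4.6.2.1.2 use the same split. The V4.0 entry in SAP section 5 records the split as a clarification.
- **Classification.** Appendix A (SAP 7.1) sorts women by baseline drug use and change in dose. It has no row for a period with no eligible days.
- **Fallback.** SAP 4.2.8.1 counts as non-responders "Subjects who cannot be assessed as responders for the co-primary efficacy endpoints, e.g. due to lack of on treatment pain data", and SAP 4.6.2.1.2 repeats this for "Subjects whose response cannot be assessed for the co-primary efficacy endpoints". Both add in brackets that this means women treated for less than 28 days. Both then give such women a change from baseline of zero.
- **Supportive analysis.** SAP 4.6.5.3 repeats both endpoints with analgesic status assessed over all days.

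**The concern.** The SAP saw that a mean over no bleeding days is undefined and repaired it for pain, but wrote no matching repair for pills in the next paragraph. Two readings then give opposite answers for the same woman.

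- **Zero pills.** She passes the DYS analgesic test whatever she took that month. This sits awkwardly beside the statement that "Increased use of EAP analgesia is a non-response in the endpoint definition".
- **Not assessable.** She is a DYS non-responder although her DYS pain score is zero.

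This is inside a co-primary endpoint. A drug that suppresses menstruation could produce more such windows on active treatment than on placebo. Protocol 11.8 keeps post-randomization bleeding data blinded, which fits that expectation but gives no rate. If the second reading were programmed, the DYS effect would be understated in the arms where bleeding had stopped. NMPP has the same gap when every recorded day is a bleeding day.

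**Working it through.** **1. The plan's own figure.** SAP 4.1 claims power above 95% for both co-primaries with 150 per group and a two-sided alpha of 0.05/2 = 0.025. I used power = Φ{[|p1−p0|√n − z√(2p̄q̄)] / √(p0q0+p1q1)} with z = 2.241.

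- NMPP (18.8% v 42.1%): (0.233×12.247 − 2.241×0.6508)/0.6296 = 2.216, power 0.987.
- DYS 75 mg (14.6% v 48.6%): 0.99999. DYS 200 mg (14.6% v 64.7%): 1.000.
- Both endpoints jointly: 0.987 under independence. The lower bound, 0.99999 + 0.98664 − 1, is also 0.987.

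The claim reproduces, so the sample size is not in question.

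**2. Which reading the text supports.**

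| Provision | Applied to a bleed-free woman with a full diary |
|---|---|
| Zero-pain rule, 4.6.2.1.1 | DYS score 0, so change = −baseline; she meets the pain criterion if baseline is at least 1.10 |
| Fallback, 4.2.8.1 and 4.6.2.1.2 | Tied to under 28 days of treatment; assigns change 0, contradicting the row above |
| Minimum of 12 diary entries, 4.6.2.1.2 | Counts completed days, so she passes |
| Pill count as a sum, 4.6.2.1.1 | A sum over no days is 0 |

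The fallback cannot be applied without contradicting the specific rule written for her. The sum definition, read alongside the zero-pain rule, gives zero pills.

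**3. Zero pills in Appendix A.** No analgesic at baseline: remains none. Ibuprofen only, or narcotic only: "Dose stopped, decreases, or is stable" covers a stopped dose. Both drugs: both stopped. Each of the four groups ends in Stable/Decrease, so the table does classify her once the count is zero.

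**4. Size under each reading.** Planning counts per 150 are 22 (placebo), 73 (75 mg) and 97 (200 mg). OR = [a/(150−a)]/[22/128]; unadjusted Wald test, raw p doubled.

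- Zero pills: nobody is removed. OR = (73/77)/(22/128) = 5.52 and (97/53)/(22/128) = 10.65.
- Not assessable, placebo unchanged, every affected woman otherwise a responder:

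| Responders lost | 75 mg OR | 200 mg OR |
|---|---|---|
| 15 (10% of arm) | 3.67 | 7.02 |
| 30 (20%) | 2.34 | 4.70 |
| 36 (24%) | 1.91, p 0.062 | |
| 60 (40%) | | 1.91, p 0.062 |

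At 35 lost on 75 mg the OR is 1.97 with p 0.045, still significant. The number of women affected is an assumption throughout.

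**5. What zero pills could hide.** Assumed example, ibuprofen only, 56 baseline days: 30 pills on 10 bleeding days and 23 on 46 non-bleeding days. That is 0.5 per non-bleeding day and 53/56 = 0.946 per day overall. A bleed-free window with 34 pills gives 34/28 = 1.214 per day.

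- DYS: zero pills, Stable/Decrease.
- NMPP: 1.214/0.5, +143%, an increase.
- All days (4.6.5.3): 1.214/0.946, +28%, an increase.

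The increase is missed by one test and caught by two.

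**6. Would an all-days rule for these women be better?** In the same example, all-days use counts as increased only above 1.15×0.946×28 = 30.5 pills. The like-for-like non-bleeding comparison flags anything above 1.15×0.5×28 = 16.1 pills. From 17 to 30 pills the all-days rule would also pass her, because her bleed-free window is set against a baseline that includes bleeding days.

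**The case for a change.** The strongest case is that a co-primary endpoint should be reproducible from the SAP without inference, and this one is not quite. No sentence names the analgesic status of a bleed-free woman, although she was foreseen. The V4.0 clarification was the obvious place for it. The fallback's example is introduced as an example, so a careful programmer might read it broadly. That all stands as a description of the text.

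The second limb is that zero pills gives a bleed-free woman an automatic pass on the DYS analgesic test, which helps the arm with more such women. This is true, but it follows from the deliberate separation by day type. A woman with one pill-free spotting day also passes, whatever she took on the other 27 days. Her other pills count in NMPP, and "Each linzagolix group will need to demonstrate a statistically significant difference for both co-primary endpoints". That requirement protects the overall efficacy claim; it does not protect the DYS estimate by itself. The DYS estimate is checked by the all-days analysis in SAP 4.6.5.3 and the overall analgesic tabulation in 4.6.2.1.2.

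One reservation runs the other way. The closing lines of SAP 4.6.2.1.2, which mention completed diaries for DYS, NMPP and analgesic use, are damaged in the available copy. A related rule may have stood there.

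**Conclusion.** No change is needed. The omission is real but small. The sum-based pill count and the parallel zero-pain rule lead to zero pills, Appendix A then gives Stable/Decrease, and the not-assessable fallback does not fit a woman with a full diary and a defined score. On that reading no responder is lost, and the planning odds ratios stay at 5.52 and 10.65. No shift in the odds ratio should be claimed. The falls shown above need the less natural reading, an unchanged placebo arm and a share of bleed-free women that the documents do not give.

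Assessing these women over all days is no clear gain. It departs from the separate assessment made explicit in V4.0, compares non-bleeding days with a mixed baseline, and creates a jump between no bleeding day and one spotting day. SAP 4.6.5.3 already supplies that view as a supportive analysis. Timing also argues against it. SAP V5.0 follows the Month 6 database lock (SAP 4.3 and 4.6.1.4), so a new classification rule for a co-primary would come late for little benefit. The same conclusion covers the mirror NMPP case.

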4.6.2.1.2. Primary Efficacy Analysis

The primary efficacy analysis will be conducted using the FAS.

The analysis of each co-primary endpoint will be conducted using a logistic regression model, with treatment group as the main effect (three values) and including the baseline pain score as a covariate. Individual linzagolix versus placebo treatment group comparisons will be made using the same logistic regression model. Estimated odds-ratios and 97.5% intervals of proportions of responders of linzagolix treatment groups versus placebo will be presented, along with Bonferroni corrected p-values. Estimates of proportions of responders with 95% confidence intervals will be presented as well, estimated at the overall mean baseline pain score.

SAS Code (may be updated at analysis stage to fit the data):

```
PROC LOGISTIC data=dataset order=internal;
Class treatment(ref=placebo) / param=glm ;
Model resp(event= "Yes")= treatment base_pain /alpha=0.05;
Oddsratio treatment ;
Lsmeans treatment / ilink exp cl alpha=0.05 at means diffs=control('1')
adjust=bon;
Ods output OddsRatiosWald=or ModelANOVA=ma ParameterEstimates=pe
lsmeans=lsm diffs=diffs;
```

Run;

In addition, the mean pelvic pain scores for DYS and NMPP and change from baseline for the last 28 days prior to Month 3 or the last 28 days of treatment (or less) for subjects who discontinued will be summarized as continuous variables by treatment group. Cumulative distribution functions (CDF) for change from baseline at Month 3 for DYS and NMPP will be provided, with separate lines for each treatment group. The x-axis will present the different values for the DYS or NMPP change from baseline, and the y-axis will present the proportion of subjects reaching each value of change. Vertical lines of the relevant MCT thresholds obtained at the Month 3 responder threshold analysis will be displayed on the plots.

The number and percentage of subjects with:

- Reduction of X for DYS,
- Reduction of X for NMPP,

Sponsor:	ObsEva		
Protocol:	18-OBE2109-003		
Document Version No.:	V5.0 Document Date: 13-JUN-2022		

- Stable or decreased use of analgesics for EAP during bleeding days, during non-bleeding days, and overall,
- Reduction of X for DYS and stable or decreased use of analgesics for EAP (during bleeding days),
- Reduction of X for NMPP and stable or decreased use of analgesics for EAP (during non-bleeding days),

will be presented.

Subjects whose response cannot be assessed for the co-primary efficacy endpoints, e.g. due to lack of on treatment pain data (i.e. subjects who received less than 28 days of treatment), will be considered as non-responders. In addition, for outputs presenting the numeric change from baseline, such subject will be assigned a change from baseline of zero. It is expected that very few subjects will be affected by these rules.

There may be missing data during the screening period and whilst under treatment, for example, missed days of completing the eDiary. The primary analyses will use observed data only in such cases, provided that a minimum number of completed daily eDiary entries are available. This effectively assumes that the individual values such as daily eDiary assessments (observed or not) are independent of being missing. Subjects who have less than the minimum number of days available will be excluded from the analysis. This is valid under the assumption that such data is MAR, conditional on the baseline value.

The required minimum number of completed daily eDiary entries will be set to 12 days of each 28-day period (two Baseline menstrual cycles and the 28-day period prior to Month 3), i.e., 43% of non-missing assessments for the primary analysis, consistent with the use of 3 days per week as the minimum number of completed diary entries as suggested in recent research ((Griffiths & al, 2018), (Cappelleri & Bushmakin, Biopharmaceutical Report, 2020), (Cappelleri & Bushmakin, Biopharmaceutical Report, 2020), (Cappelleri & Bushmakin, Biopharmaceutical Report, 2020), Cappelleri & Bushmakin, Biopharmaceutical Report, 2020), (Cappelleri & Bushmakin, Biopharmaceutical Report, 2020), completed daily eDiaries for DYS, NMPP and analgesic use.

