13.4 ANALYSIS SETS

The following data sets will be used for the statistical analysis:

1. **Safety Set:** All randomized subjects who received at least one dose of double-blind study drug irrespective of the treatment received. Subjects will be analyzed according to treatment received.

2. **Full Analysis Set (FAS):** All randomized subjects who received at least one dose of double-blind study drug irrespective of the treatment received. This is the same as the Safety Set, but for the FAS subjects will be analyzed according to randomized treatment.
3. **Per Protocol (PP) Set:** All randomized subjects who completed the six months of treatment excluding those identified as having major protocol deviations that could potentially affect the efficacy assessments up to Month 6. Subjects will be analyzed according to randomized treatment.
4. **Follow-up (FU) Set:** All randomized subjects who completed the six months of treatment and entered the drug free follow-up period. Subjects will be analyzed according to randomized treatment.
5. **Pharmacokinetic (PK) Set:** all subjects who received active study medication, had no major protocol deviations impacting PK and with available PK data.

Individual data points may also be excluded from the analysis sets. Rules for such exclusions will be described in the statistical analysis plan (SAP), including, where appropriate, time windows for various safety and efficacy analyses. In general, analyses of efficacy will be conducted using the FAS and PP sets, analyses of safety will be conducted using the Safety Set and analyses of PK will be conducted using the PK Set.

A sub-group analysis will be performed for the secondary endpoint of dyspareunia as described in Section 13.5.3.5. Additional pre-planned sub-group analyses will be described in the SAP.

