13.5.8 Missing Data

Summary statistics will be based primarily on non-missing values. The planned statistical analyses aim to estimate the efficacy of linzagolix versus placebo whilst under randomized treatment and therefore lack of data after treatment discontinuation will not be considered as missing for these analyses.

Subjects who cannot be assessed as responders or not for the co-primary efficacy endpoints, e.g. due to lack of enough on treatment pain data will be considered as non-responders. In addition, for endpoints assessing the numeric change from baseline, such subjects will be assigned a change from baseline of zero. It is expected that very few subjects will be affected by these rules.

As additional analyses, in order to estimate the effect of treatment policy, a reference based multiple imputation approach will be used for the co-primary endpoints for subjects who discontinue the study early under the assumption that the efficacy of the linzagolix treated subjects gradually transitions to that observed in the placebo subjects.

There may be missing data during the screening period and whilst under treatment, for example, missed days of completing the eDiary. The primary analyses will use observed data only in such cases provided that a minimum number of completed daily eDiary entries are available. This effectively assumes that the individual values such as daily eDiary assessments (observed or not) are independent of being missing.

Further details on the handling of missing values and the methods and planned sensitivity analyses to check the robustness of the analysis results under alternative assumptions with regards to missing data will be provided in the SAP.

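### The SAP removes subjects with sparse on-treatment diaries from the co-primary and numeric diary analyses, where the protocol counts them as non-responders or zero change, and Section 5 does not declare it

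*SAP*

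**What the plan says.** Protocol 13.5.8 states that subjects who cannot be classified on the co-primary endpoints, for example "due to lack of enough on treatment pain data will be considered as non-responders". For numeric change endpoints the same subjects receive a change of zero. The section also makes use of observed diary data conditional on a minimum number of entries. It does not give the number or say that subjects below it are dropped. It leaves to the SAP "Further details on the handling of missing values and the methods and planned sensitivity analyses". Protocol 13.4 adds: "Individual data points may also be excluded from the analysis sets".

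SAP 4.2.8.1 and 4.6.2.1.2 repeat the non-responder and zero-change rule without the word *enough*, and gloss it in 4.2.8.1 as "e.g. due to lack of on treatment pain data (i.e. subjects who received less than 28 days of treatment". SAP 4.6.2.1.2 then sets a second rule. "The required minimum number of completed daily eDiary entries will be set to 12 days of each 28-day period", and "Subjects who have less than the minimum number of days available will be excluded from the analysis". The justification is: "This is valid under the assumption that such data is MAR, conditional on the baseline value". The same section opens with "The primary efficacy analysis will be conducted using the FAS". SAP 4.6.3 repeats the exclusion, with the same assumption, for the ranked secondary endpoints taken from the daily diary.

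**The concern.** The protocol and the SAP give different outcomes for the same subject: one who stays on treatment but completes fewer than 12 of the 28 diary days before Month 3. The protocol keeps her as a non-responder; the SAP removes her.

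How well a subject keeps her diary after randomisation may depend on pain relief, worsening, side effects or arm. If it does, removing her can bias the randomised comparison in either direction. If missingness is at random given baseline, it does not. The co-primary result depends on which is true. A reader who goes to SAP Section 5 for departures from the protocol would not learn that this rule had changed.

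**Working it through.** **1. Do the rules conflict?** The protocol ties its outcome to a lack of *enough* on-treatment pain data. The SAP's gloss, under 28 days of treatment, is a different condition. Protocol 13.5.2 already says that subjects who stop within four weeks are assessed on the fewer days they have. Short exposure therefore cannot be all that *not enough data* means. A subject below the diary minimum fits the protocol's wording, and the SAP gives her a different outcome.

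**2. Was this delegated?** Protocol 13.5.8 leaves the number of days to the SAP, so choosing 12 (12/28 = 42.9%, matching the SAP's 43%) is within its remit. Replacing the outcome that the same section states is not clearly so. Protocol 13.4 speaks of data points, not subjects.

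**3. Is it declared?** SAP 1.2 undertakes to outline differences from the protocol. The opening of Section 5 lists one, the end of the Month 6 window. No row of the amendment table declares the exclusion. One V2.0 row mentions a diary minimum, but only as the reason for deleting a protocol-deviation category.

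**4. Does any planned analysis test it?** SAP 4.6.2.2 offers a CMH test and a wider analgesic definition; neither changes the handling of sparse diaries. By their text, SAP 4.6.5.1 (non-responder) and 4.6.5.2 (multiple imputation) cover only subjects who discontinue. The code in 4.6.5.2 carries no such restriction and runs on the FAS, so as written it would impute any missing value from the placebo arm. Text and code leave it open whether an on-treatment subject with a sparse diary is covered.

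**5. How much could it matter?** Inputs from Protocol 13.2 and SAP 4.1: 150 per arm; two-sided alpha 0.05/2 = 0.025 per comparison; NMPP 42.1% v 18.8%; DYS (75 mg) 48.6% v 14.6%. The power formula for two proportions uses pooled variance under the null.

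The plan's own figure first. With no shortfall, power is 98.66% for NMPP and above 99.99% for DYS. Joint power is at least the sum minus 1, or 98.66%, which agrees with the stated figure of more than 95%.

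Let *m* be the assumed fraction of an arm below 12 days, and take the planning rate *p* as the rate among assessable subjects.

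- Protocol rule: rate = p(1 − m), n = 150.
- SAP exclusion: rate = p, n = 150(1 − m).

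Example, NMPP, 15% active and 5% placebo: 0.421 × 0.85 = 0.3579; 0.188 × 0.95 = 0.1786; OR = (0.3579/0.6421)/(0.1786/0.8214) = 2.56. Under exclusion n = 127.5 and 142.5, and the OR is 3.14.

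| NMPP shortfall, active/placebo | Rates, protocol rule | OR, protocol rule (exclusion 3.14) | Power, protocol rule | Power, exclusion |
|---|---|---|---|---|
| 2%/2% | 0.4126 v 0.1842 | 3.11 | 98.4% | 98.5% |
| 5%/5% | 0.3999 v 0.1786 | 3.07 | 98.0% | 98.2% |
| 3%/1% | 0.4084 v 0.1861 | 3.02 | 97.9% | 98.5% |
| 1%/3% | 0.4168 v 0.1824 | 3.20 | 98.8% | 98.5% |
| 15%/5% | 0.3579 v 0.1786 | 2.56 | 90.1% | 97.6% |
| 5%/15% | 0.3999 v 0.1598 | 3.50 | 99.3% | 97.6% |

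For DYS the OR is 5.53 under exclusion. Under the protocol rule it is 5.45 (2%/2%), 4.37 (15%/5%) and 6.05 (5%/15%), with power at least 99.9% throughout.

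**The case against.** The best defence is that Protocol 13.5.8 treats unassessable subjects and missed diary days in separate paragraphs, never says what follows below the minimum, and leaves the detail to the SAP. On that reading the SAP fills a gap openly, with its assumption and sources stated. This does not survive the word *enough*, nor the treatment of short exposure in Protocol 13.5.2. It is true, however, that the rule is visible in SAP 4.6.2.1.2 and 4.6.3; what is missing is its declaration as a departure.

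Second, the calculation does not show that the protocol rule is better. On its own assumption exclusion returns 3.14 every time, and the protocol rule moves the estimate, sometimes in the drug's favour. That stands. The case for the protocol rule is that it was pre-specified and keeps every randomised, treated subject, not that exclusion has been shown to be biased.

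Third, shortfall is probably rare. Subjects must complete 75% of diary days in screening (Protocol 9.2.1), the diary has a daily alarm (Protocol 10.3.2), and 12 of 28 days is lenient. That also stands, and it limits the likely size.

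Finally, the SAP code is marked as open to updating, and a reader might guess that the short-exposure rule governs a subject who meets both conditions. These are minor points, but the SAP does not settle either.

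**Conclusion.** The concern holds. The SAP replaces a protocol outcome with exclusion from the co-primary and numeric diary-based ranked analyses, does so within an analysis labelled FAS, and neither gives a reason nor lists the change. No analysis whose text covers subjects still on treatment applies the protocol rule.

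At 2% to 5% shortfall, equal in both arms, the NMPP odds ratio moves from 3.14 to between 3.07 and 3.11, and power changes by about 0.2 points or less. A 15% v 5% imbalance takes it to 2.56 or 3.50 according to direction. All shortfall rates are assumptions, and the figures take the planning rates as holding among assessable subjects. They show that the two rules can give different answers, not that exclusion is biased. This should be fixed, though it is unlikely by itself to overturn the primary result.

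**What to change.** - **Preferred, while the blind holds.** For fewer than 12 completed on-treatment days, apply the Protocol 13.5.8 rule as primary: non-responder for the co-primaries, zero change for numeric diary endpoints. Apply zero change within each endpoint's own population, for example baseline mean above 1 for dyspareunia (SAP 4.6.3.5). Keep the exclusion as a labelled sensitivity analysis.
- **If exclusion stays primary, or the blind has been broken.** SAP V5.0 already reports thresholds from the Month 6 lock (4.6.1.4), after which SAP 4.3 allows unblinded results to reach the sponsor. Changing the primary rule after that would be post hoc. Declare the exclusion in Section 5 with a reason and report the protocol rule alongside it.
- **Either way.** State which rule governs a subject with both short exposure and a sparse diary. Make the text and code of SAP 4.6.5.2 agree on sparse-diary subjects who do not discontinue. Report the number affected by arm and endpoint.

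The cost is one extra run of the co-primary and numeric diary models, one table of counts and one Section 5 entry. Response rates may be slightly lower under the protocol rule, and the odds ratio may move either way.
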